5.3.2 Bleeding, Cramping, and Other Contraceptive Use

For the categories of bleeding, cramping and other contraception use, no imputation of data from the diaries will be done for missing data. For example, a subject with completely missing data for a particular diary day will be considered as having no reported bleeding, no cramping, no other contraceptive use, etc. for that day. Missing data for, say, bleeding alone will be considered as the subject having no reported bleeding for that day.

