5.2 Data Handling

5.2.1 Conventions

Percentages will be based on available data, and denominators will generally exclude missing values.

The precision of the original measurements will be maintained in summaries and listings, when possible. Generally, means, medians and standard deviations will be presented with an increased level of precision as follows: means and medians will be presented to one more decimal place than the raw data, and the standard deviations will be presented to two more decimal places than the raw data.

Summaries of continuous variables that have some values recorded using approximate values (e.g. < or >) will use imputed values. The approximate values will be imputed using the closest exact value for that measurement. Listings will present the data in the original format.

For tables where rounding is required, rounding will be done to the nearest round-off unit. For example, if the round-off unit is the ones place (i.e., integers), values $\geq XX.5$ will be rounded up to $XX+1$ while values $< XX.5$ will be rounded down to XX .

For frequency counts of categorical variables, categories whose counts are zero will be displayed for the sake of completeness. For example, if none of the subjects discontinue due to “lost to follow-up,” this reason will be included in the table with a count of 0. Categories with zero counts will not have zero percentages displayed.

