5.3 Handling of Dropouts or Missing Data

Unless otherwise specified, missing data will not be imputed. Subjects who drop out will not be replaced and all available data will be used.

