5.3.1 Diary Data

Daily diary entries by the subject are made directly onto paper CRFs and are, therefore, "self-sourcing" source data. If a subject does not bring the original (O) diary to the clinic visit, then the site will ask the subject to recall the data on a diary copy (C). The copy will be used until the original is returned at a following clinic visit. During the first 24 months of the study, the diary data for bleeding, cramping and other contraception use will be recorded by the subject on a daily basis. Beginning after month 24, the subject will continue to record other contraception use on a daily diary but bleeding and cramping information will be characterized on a bleeding/cramping form completed by the site through subject interview approximately every 3 months.

If the original diary becomes available after the data from the copy have been entered into the study data base, the data base will be updated to include the original diary data along with the copy. The data base audit trail will reflect initial data entry from the copy followed by subsequent entry of the original. Diaries returned by the subject that include days when no information was obtained have those data records included in the data base. However, no such blank records are in the data base for entire diary pages that may have not been returned, e.g., the subject may have returned diaries for March and May but never returned the April diary. In these cases, missing data are not part of the data base but are accounted for as blank records in the same manner as those which appear, essentially at random, within a returned diary. Since the diary day counting process for identification of 28-day cycles when another birth control method use was reported looks at each diary date record relative to the IUS insertion date, the presence of missing diary records will not affect this calculation. The extent and magnitude of missing diary records will be assessed and presented as part of overall diary results.

Diary numbers on CRFs will not be used; only the date information on the CRF will be used. If the date recorded does not exist, the data will not be included. If the subject never returns the original copy, the copy will be used for analyses. Duplicate diary records (e.g., an original and a clinic copy) for the same study day can appear in the study data base and should be handled as follows:

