- Subject incidence of TEAEs by MedDRA system organ class, preferred term, and closest relationship to IUS (Related/Not Related). At each level of subject summarization a subject is classified according to the closest relationship if the subject reported one or more events. Related will be defined as “Related”, “Probably Related”, or missing. Not related will be defined as “Unlikely Related” or “Not Related”
- Subject incidence of TEAEs by MedDRA system organ class, preferred term, and closest relationship to IUS Procedure (Related/Not Related). At each level of subject summarization a subject is classified according to the closest relationship if the subject reported one or more events. Related will be defined as “Related”, “Probably Related”, or missing. Not related will be defined as “Unlikely Related” or “Not Related”
- Subject incidence of serious TEAEs and total number of unique serious TEAEs by MedDRA system organ class and preferred term

Incidence rates will include in the denominator all subjects in the Safety Population.

Missing Severity or Relationship

Missing severity or relationship to study drug will prompt queries to be sent to the investigators to provide the information. If after query resolution, the information remains missing, the following conventions will be used in summary tables.

- An event with missing severity will be considered Severe.
- An event with missing relationship will be considered related to study drug.

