11.6 Diary Reported Bleeding and Cramping/Pain Analysis

11.6.1 Months 1-24

For each 28-day cycle and each 84 and 90 day interval post-insertion, the incidence of on-treatment cramping/pain (none, mild, moderate, severe) and bleeding (none, spotting, light flow, medium flow, heavy flow) will be calculated based on diary entries and presented by treatment group. Summaries of the following types will be presented:

- Incidence of cramping/pain by 28-day cycle and 84 and 90 day intervals post-insertion (none vs. ≥ 1 day; 1-3, 4-7, >7 , and >20 days)

- Incidence by of bleeding by 28-day cycle and 84 and 90 day intervals post-insertion (none vs. spotting vs. bleeding; none vs. ≥ 1 day; 1-3, 4-7, >7 , and >20 days; no bleeding vs. any bleeding)
- Incidence of cramping/pain by highest severity or bleeding by greatest intensity by cycle and 84 and 90 day intervals post-insertion. At each level of subject summarization a subject is classified according to the highest severity or intensity if the subject reported one or more events.

Descriptive continuous-based statistics (mean, standard deviation, median, minimum, maximum) will be used to summarize the number of days of reported cramping and bleeding and/or spotting during each 28-day cycle and each 84 and 90-day interval. The number of spotting days and the number of bleeding days (light flow, moderate flow, heavy flow combined and each category separately) will also be summarized using this approach. For cramping/pain, this will also be presented within each severity rating, i.e., the total number of reported days will be broken down into the number of days of mild, moderate, and severe cramping/pain.

11.6.2 After Month 24

The incidence of reported cramping every three months after Month 24 will be reported using the categories which appear in parentheses below:

- Over the last 3 months has the subject had any menstrual cramping/pain? (Yes/No)
- Did the cramping/pain occur mainly when the subject was having any bleeding or spotting? (Yes/No)
- The worst cramping/pain experienced during these months (mild, moderate, severe)

The incidence of bleeding and/or spotting will be presented in a similar fashion based on the following questions and categories of response:

- Over the last 3 months has the subject had any menstrual bleeding/spotting?
- What was the main pattern of bleeding/spotting the subject experienced for these months? (Just Spotting, Irregular Bleeding, Regular Bleeding [periods])

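### Blank diary days count as no bleeding and no cramping, with no minimum of recorded days, so from this rule Months 1–24 day counts are too low or unchanged and 'none' is too large or unchanged

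*SAP*

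**What the plan says.** - **Blank days and items.** SAP 5.3.2 states that diary data are not imputed, but then fixes a value: a subject with "completely missing data for a particular diary day will be considered as having no reported bleeding, no cramping, no other contraceptive use" for that day. A day on which only the bleeding item is blank is scored as no bleeding. That case is given as an example, so a blank cramping item falls under the same rule.
- **Unreturned pages.** For whole pages that never came back, SAP 5.3.1 says that "missing data are not part of the data base but are accounted for as blank records", in the same manner as blanks inside a returned diary. It describes the latter as arising essentially by chance.
- **Disclosure.** SAP 5.3.1 also promises: "The extent and magnitude of missing diary records will be assessed and presented as part of overall diary results". It gives no expected rate and no threshold.
- **Summaries.** Under SAP 11.6.1, incidence for Months 1–24 "will be calculated based on diary entries and presented by treatment group". One item listed is "Incidence by of bleeding by 28-day cycle and 84 and 90 day intervals post-insertion", split into none versus any and into day-count bands. Worst severity and mean and median numbers of days are also reported. No minimum of recorded days is set. The 23-day threshold in SAP 5.5 and 9.2 concerns the length of the last cycle of use for efficacy, not diary completeness.
- **General conventions.** SAP 5.2.1: "Percentages will be based on available data, and denominators will generally exclude missing values". SAP 5.3: "Unless otherwise specified, missing data will not be imputed". Both leave room for an exception, but 5.3.2 gives no reason for making one.

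**The concern.** Not recording a symptom is different from not having one. Under the rule, a woman who loses a month's page contributes a symptom-free month. A woman who skips entries contributes fewer bleeding days than she had. Nothing in SAP 11.6.1 stops a sparsely completed cycle or interval from being classified as 'none' or from receiving a low worst-severity grade.

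Bleeding pattern is a named secondary objective in both documents. No formal tests are planned, so the descriptive figures are themselves the result. The LNG20 day counts and 'none' rates are what readers will take away. Applying the same rule to Mirena does not correct the absolute LNG20 figures.

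**Working it through.** The documents state no figure on this point, so there is none to reproduce. All missingness rates below are assumptions.

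**Inputs.** The scoring rules are from SAP 5.3.1, 5.3.2 and 11.6.1. A 'none' rate of 20% over 90 days is used as the illustration; Protocol 7.1.7 cites about 20% with amenorrhea of 90 days or more by the end of year 1. The assumed missing shares are 5%, 10% and 20%.

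**1. Direction.** On each day the true value is 0 or 1, and a blank is scored 0. So scored days ≤ true days in every interval, and a true 'none' stays 'none'. By the same argument, worst severity can only fall or stay the same. Middle bands can move either way: 5 true days with 2 blanked enter the 1–3 band, while 2 true days both blanked leave it.

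**2. Day counts, blanks at random.** Expected count = d × (1 − m). For d = 10: 9.5, 9.0 and 8.0 at m = 5%, 10% and 20%.

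**3. None versus any, scattered blanks.** With 18 of 90 days blank (20%), P(false 'none') = C(90 − d, 18 − d) / C(90, 18):
- d = 1: 18/90 = 20%
- d = 2: (18 × 17)/(90 × 89) = 306/8,010 = 3.8%
- d = 5: (18 × 17 × 16 × 15 × 14)/(90 × 89 × 88 × 87 × 86) = 0.000195, about 0.02%

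**4. None versus any, one 30-day page lost in a share f of 90-day intervals.** The true 'none' rate is 20%.
- One 5-day episode per bleeder: 26 of 86 possible starts lie wholly inside the page, 26/86 = 0.302. Reported 'none' = 0.20 + f × 0.80 × 0.302.
- Two 5-day episodes at least one day apart: C(21,2)/C(81,2) = 210/3,240 = 0.0648. Reported 'none' = 0.20 + f × 0.80 × 0.0648.
- Independent months: 'none' over two recorded months = 0.20^(2/3) = 0.342. Reported 'none' = (1 − f) × 0.20 + f × 0.342.

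| Assumed pattern | f = 5% | f = 10% | f = 20% |
|---|---|---|---|
| Two episodes | 20.3% | 20.5% | 21.0% |
| Independent months | 20.7% | 21.4% | 22.8% |
| One episode | 21.2% | 22.4% | 24.8% |

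The 0.342 is the same if only recorded days are used, so a recorded-days denominator alone does not repair the 'none' rate.

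**5. Intervals with no entries at all.** If a share w of intervals had no diary and these counted as 'none', reported 'none' = 0.20 + 0.80 × w: 24%, 28% and 36% at w = 5%, 10% and 20%. SAP 11.6.1 works from diary entries and does not say whether they count.

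**6. Limits of counting over recorded days.** If every blank falls on an event-free day, a true 10 per 90 becomes 10/85.5 × 90 = 10.5, 10/81 × 90 = 11.1 and 10/72 × 90 = 12.5 at 5%, 10% and 20% blank, while blank-as-none is exactly right. If 4.5 of 90 days are blank and all were bleeding days, blank-as-none gives 5.5 and recorded-days 5.5/85.5 × 90 = 5.8; both are too low.

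**7. Completeness share.** Losing a calendar-month page of 28 to 31 days leaves (90 − 28)/90 = 68.9% down to (90 − 31)/90 = 65.6%. A share just above 69% screens that out. It does not catch a 30-day page split 15/15 across two intervals (75/90 = 83% each), nor 8 blanks in a 28-day cycle (20/28 = 71%), which can hide a 5-day episode.

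**8. Pearl Index.** If 1% of counted cycles should have been excluded for unrecorded use of another method (10% × 10%, both assumed), 0.280 becomes 0.280/0.99 = 0.283.

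**9. Timing.** The planned end of recruitment, April 2013, plus 24 months gives April 2015.

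**The case against.** The SAP speaks of reported symptoms and commits to showing how much diary data is missing, so a reader will see both the counts and the gaps. Sites review diaries at visits and collect recall copies, which should reduce blanks. The outcome is descriptive. Counting over recorded days swaps one unverifiable assumption for another (step 6). All of this stands. It is why the alternative belongs beside the existing summary rather than in its place. It does not change how a remaining blank is scored, and disclosure neither corrects nor bounds the error.

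Three stronger readings are tempting but unsupported:

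- **That the published counts must be too low.** With complete diaries, or with blanks only on symptom-free days, there is no error. The one-way direction covers this rule only. SAP 5.3.1 also codes the early diary's undifferentiated bleeding entry as normal flow, which can raise that category, and recall copies can err either way.
- **That the SAP contradicts its own cautious handling of adverse events.** SAP 11.2 says "An event with missing severity will be considered Severe", but that concerns an event known to have happened whose grade is missing. A blank diary day leaves open whether anything happened, so the comparison does not hold.
- **That percentages of days are distorted throughout.** The protocol synopsis asks for percentages of days for bleeding and dysmenorrhea, and Protocol 9.8 for dysmenorrhea. SAP 11.6.1 lists incidence and day counts, and the SAP takes precedence.

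**Conclusion.** The concern holds in limited form. From the blank-as-none rule alone, Months 1–24 total bleeding and cramping days are too low or unchanged, and 'none' is too large or unchanged; middle bands can go either way. The size cannot be stated, because no missingness rate is documented.

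Under the assumed rates, day counts fall in proportion to random blanks. Scattered blanks affect none-versus-any only for women with very few event days. Lost pages matter more: at f = 10% the 'none' rate rises by 0.5 to 2.4 percentage points. Intervals with no entries could matter most, but only if they count as 'none', which the SAP leaves open.

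A reader might infer that efficacy is compromised. It is not to any material degree: the Pearl Index moves by about 0.003 in the illustration. A supplementary analysis is still worth having. It follows the SAP's own denominator convention and its description of blanks within returned diaries as chance events, and it needs no new data.

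**What to change.** Keep the existing blank-as-none summary. Beside it, add a supplementary analysis in SAP 5.3.2 and 11.6.1 that:

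1. treats each blank item as missing, bleeding and cramping separately, including items on partly completed days and on unreturned pages;
2. computes day counts and percentages over the days recorded for that item, stating that this assumes blanks are unrelated to bleeding or cramping and that it overstates days if blanks fall on event-free days;
3. classifies a cycle or interval as 'none', or by worst severity, only if a pre-set share of its days is recorded, with a second share as a sensitivity analysis. The text should note that a share just above 69% excludes only a 90-day interval that lost a whole calendar-month page, not a page split across two intervals or a shorter gap in a 28-day cycle;
4. shows the number of evaluable women per cycle and interval;
5. states that cycles and intervals with no entries are not evaluable, rather than 'none'.

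The shares are the sponsor's choice and should be fixed before the next data cut-off. On the planned dates the Months 1–24 diaries were complete about April 2015, so the data were probably already collected. Label the analysis by when it was specified.

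The cost is SAP wording, some programming, one added set of tables, fewer evaluable intervals and slightly higher reported bleeding. No change to the Pearl Index is needed.

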5.3.3 Missing Adverse Event Start and Stop Dates

For adverse events (AE), the following rules for imputing values for missing start dates are used:

- If the AE start date field includes a SAS missing value (e.g., .N) or is completely missing, the start date is set to the IUS insertion attempt date. This conservatively assumes that the AE began on the same date when insertion was first attempted.
- If the AE start date field is missing day only, set it equal to the first day of the recorded month and year.
- If the AE start date field is missing day and month only, set it equal to the first day of January of the recorded year.
- Any resultant imputed AE start date that is earlier than the IUS insertion attempt date is set equal to the IUS insertion attempt date. This also conservatively assigns the AE as having occurred on the same date as the IUS insertion attempt.
- If the AE stop date is completely missing, the event will be noted as “Continuing” in the stop date column in the AE listings.
- If the AE stop date field is missing day only, set it equal to the 15th day of the recorded month and year
- If the AE stop date field is missing day and month only, set it equal to the 31st day of December of the recorded year.

- If the AE stop date field is missing month only, set it equal to December of the recorded year.
- A resultant imputed AE stop date that is earlier than the AE start date is set equal to the AE start date. This ensures that all AEs have a minimum duration of one day.

5.3.4 Missing Concomitant Medication Start and Stop Dates

For concomitant medications (CM), the following rules for imputing values for missing start dates are used:

- If the CM start date field includes a SAS missing value or is completely missing, the start date is set to the IUS insertion attempt date.
- If the CM start date field is missing day only, set it equal to the first day of the recorded month and year.
- If the CM start date field is missing day and month only, set it equal to the first day of January of the recorded year.
- If the CM stop date field includes a SAS missing value or is completely missing, the stop date is set to the last date of known product use.
- If the CM stop date field is missing day only, set it equal to the 15th day of the recorded month and year
- If the CM stop date field is missing day and month only, set it equal to the 31st day of December of the recorded year.
- If the CM stop date field is missing month only, set it equal to December of the recorded year
- Any imputed CM stop date that is before the insertion attempt date implies the CM was a Pre-Trial Medication. Any medication started on or after the insertion attempt date or any medication started before insertion but ending on or before the last known date of product use is a Concomitant Medication.

5.3.5 Missing Dates for Other Events, Including Return to Menses, Return to Fertility, Pap Tests, Date of IUS Expulsion/Removal, and Reported Pregnancies

For missing dates of other events, any date that is completely missing or contains the year only will be set to the date of the subject's last clinic visit. If a month and year are recorded but the day is unknown, the day will be set to the first day of the month. If this

results in an imputed date that is earlier than the last clinic visit, the date will be set to the date of the last clinic visit.

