6.3 Screening/Enrollment Visit

Screening is considered to start with the signing of the Informed Consent Form by the subject. Although the Screening and Enrollment Visits may occur during one visit, the Screening procedures may be performed over multiple days. The Enrollment Visit is considered to be on the date the subject is assigned through the IVRS. Screening test results are not required to be available prior to the Enrollment Visit.

Scheduling of the Enrollment Visit must take the following schemes into account:

- When switching from an oral, transdermal or vaginal hormonal contraceptive, the subject should continue that method after the study IUS insertion until the end of the current cycle. If using the contraceptive continuously (without a hormone free interval), then discontinue 7 days after IUS insertion. When possible, the Enrollment Visit should be scheduled during the hormone-free time of the cycle (i.e., “placebo week,” “patch-free week,” or “ring-free week”)
- When switching from an injectable monthly combined hormonal injection, the study IUS insertion may occur anytime within 28 days of the last injection
- When switching from non-hormonal contraception (except copper IUD), the study IUS insertion **must** be performed within the first 7 days of the menstrual cycle

- When switching from a contraceptive implant, another hormonal IUS, or a copper IUD, the study IUS insertion may occur anytime in the menstrual cycle but should occur on the same day as removal of the implant, non-study IUS, or IUD
- Women who need a screening Pap test (see section 6.11) should be scheduled for screening on a day they are expected to have minimal or no bleeding
- All enrollment procedures must be completed within 30 days of screening. If greater than thirty days, Medical Monitor approval must be obtained before rescreening or enrollment

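### Setting a day-missing medication stop date to the 15th, with no floor at the drug's start and no bound at insertion, can make a drug used after a late-month insertion both pre-trial and concomitant

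*SAP*

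**What the plan says.** SAP 5.3.4 gives the imputation rules for medication dates. For a stop date lacking only the day: "If the CM stop date field is missing day only, set it equal to the 15th day of the recorded month and year". For a start date that is completely missing, "the start date is set to the IUS insertion attempt date".

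The last bullet of 5.3.4 classifies the records in two sentences. The first reads: "Any imputed CM stop date that is before the insertion attempt date implies the CM was a Pre-Trial Medication". The second has two limbs. "Any medication started on or after the insertion attempt date" is concomitant, and "any medication started before insertion but ending on or before the last known date of product use is a Concomitant Medication". Nothing says which sentence wins when both apply.

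SAP 5.3.3 uses the same mid-month convention for adverse events but adds a guard: "A resultant imputed AE stop date that is earlier than the AE start date is set equal to the AE start date". Section 5.3.4 has no such line.

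Protocol 6.3 tells women switching from an oral, transdermal or vaginal hormonal method that "the subject should continue that method after the study IUS insertion until the end of the current cycle"; with continuous use they "then discontinue 7 days after IUS insertion". Protocol 5.6 allows this first-month use and requires all concomitant medications on the Concomitant Medication form. Protocol 9.6 and SAP 8.1 define a concomitant medication by use during the active treatment period. Protocol 9.6 tabulates the two classes separately.

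**The concern.** An imputation rule should not produce a date that the record itself rules out, and it should not move a drug across the boundary that the tables are built on. Here it can do both. A drug begun on the insertion day, the 20th, and stopped later that month on an unrecorded day is given a stop on the 15th, five days before it started. A hormonal method known to have continued past a late-month insertion is given a stop before insertion and so meets the pre-trial sentence, although under Protocol 9.6 and SAP 8.1 it was taken during treatment.

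At stake is the medication summary around insertion: overlapping hormone use in the first cycle, and short courses started at or just after insertion. Because two sentences conflict, two programmers working from the same text could also build different tables. SAP 8.1 describes a summary only for concomitant medications, so on its wording a record labelled pre-trial might appear in no specified table. Protocol 9.6 would still show it, but under pre-trial.

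**Working it through.** The documents give no figure to reproduce. The check applies the 5.3.4 rules literally.

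**Worked cases: insertion on 20 March, stop day missing**

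| Drug (true dates) | Imputed stop | Stop before own start? | Pre-trial sentence | Concomitant sentence |
|---|---|---|---|---|
| Pill, 1 January to 27 March | 15 March | No | Applies | Applies (started before insertion, ended by last known use) |
| Analgesic, 20 to 22 March | 15 March | Yes | Applies | Applies (started on or after insertion) |
| Antibiotic, 25 to 30 March | 15 March | Yes | Applies | Applies (started on or after insertion) |
| Pill, 1 January to 3 April | 15 April | No | Does not apply | Applies |

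The first three records meet both definitions. The fourth is unaffected because its stop month is later than the insertion month.

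**How often the pre-trial sentence applies**

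Inputs:
- Recruitment window November 2009 to April 2013 (Protocol synopsis, planned study dates): 42 months, 24 of 31 days, 14 of 30, three of 28 and one of 29. Total 744 + 420 + 84 + 29 = 1,277 dates.
- Assumption: insertion is equally likely on each date. The documents do not give the distribution.
- Condition: the drug's stop day is missing.

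For a true stop k days after insertion in a month of L days, the sentence applies when the insertion day is after the 15th and insertion day + k is still in that month. The number of such insertion days is max(0, L − k − 15). Summed over the 42 months:

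| k (days) | Count of insertion dates | Share of 1,277 |
|---|---|---|
| 0 | 1,277 − 42 × 15 = 647 | 50.7% |
| 1 | 1,277 − 42 × 16 = 605 | 47.4% |
| 3 | 1,277 − 42 × 18 = 521 | 40.8% |
| 7 | 1,277 − 42 × 22 = 353 | 27.6% |
| 14 | 24 × 2 + 14 × 1 = 62 | 4.9% |
| 21 or 28 | 0 | 0% |

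**Which repair works**

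- Floor at the start date, stop = max(15th, start): a drug started on or after insertion can no longer have a stop before insertion (0%). A hormonal method begun 21 or 60 days before insertion still meets the pre-trial sentence on 27.6% of dates for a stop 7 days after insertion. Whenever the sentence applies at k = 7, insertion falls between the 16th and the 24th, so a start 21 days earlier is on or before the 3rd and the floor changes nothing.
- Last day of the recorded month: 0% at every k in the table, because the imputed stop cannot precede an insertion in that month.

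So there are two separate defects. The missing floor produces the impossible dates. The mid-month stop, not bounded at insertion, mislabels the continued hormonal method.

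**The case against.** The strongest reply is that the SAP already classifies these records correctly. The second sentence of the bullet makes any drug started on or after insertion concomitant. Read literally, it also covers a drug started earlier that ended by last known use, and the definition in Protocol 9.6 and SAP 8.1 points the same way. This stands to the extent that a reader who infers that all such drugs become pre-trial goes too far. It does not remove the conflict. The pre-trial sentence covers the same records without exception. The second limb is also too wide: it sets no lower limit on the stop date, so it takes in drugs that truly ended before insertion.

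Three other strong readings are tempting and not supported:
- *Half of the records are wrong.* The 51% is the share of insertion dates after the 15th. It is the affected share only for a stop on the insertion day with the day missing, and it falls quickly with later stops. Protocol 6.3 also prefers enrollment in the hormone-free part of the cycle, and nothing in the documents shows how often a continued method ends in the insertion month.
- *Adding the adverse-event guard would cure the hormonal case.* It would not, as shown above.
- *Efficacy is affected.* SAP 5.5 takes other contraceptive use for the Pearl Index cycle exclusions from the daily diaries alone, so a misfiled medication record cannot change that result.

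It is also fair to say that the 15th is the SAP's own convention for day-missing stop dates, used for adverse events too. The convention is not wrong in itself. The trouble is its use in the insertion month, where the same date decides the classification. Insertion-related local anesthesia and cramping have their own summaries (SAP 11.3 and 11.8), though these do not cover oral analgesics.

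**Conclusion.** The point holds as a minor defect in a stated rule. When insertion is after the 15th and the recorded stop month is the insertion month, 5.3.4 imputes a stop before insertion and, for drugs started after the 15th, before their own start. The record then meets two contradictory definitions with no precedence. Given a missing stop day and uniform insertion dates, the pre-trial sentence applies on about 51% of insertion dates for a same-day stop, 28% at 7 days, 5% at 14 days and 0% at 21 days or more. These are conditional shares, not error rates. How many records lack a stop day is unknown, and the final label depends on which sentence the programmer follows. The effect is confined to the descriptive pre-trial and concomitant medication tables.

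**What to change.** Amend SAP 5.3.4 in four places:
- Never let an imputed medication stop date precede the medication start date, matching 5.3.3.
- When the recorded stop month is the insertion month and the day is missing, impute the last day of that month, capped at the data cut-off. At the least, impute no earlier than the insertion attempt date.
- State that a drug started on or after the insertion attempt date is concomitant, whatever its imputed stop.
- Limit the clause on drugs started before insertion to those whose stop is on or after insertion, so that it no longer overlaps the pre-trial sentence.

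The cost is a few sentences and a little code. The downside is that a few drugs truly stopped before insertion in that month will be listed as concomitant. For a record that cannot settle the question, this is the safer direction of error.
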